- 3.23 Existing implantable medical electronic devices, life-supporting medical devices, and medical monitoring devices.
Note: Metal implants for orthopedic repair, e.g. pins, clips, plates, cages, joint replacements are allowed, as are central venous access devices.
- 3.24 History of myocardial infarction or ischemic heart disease within the past six months.
- 3.25 History of epilepsy, brain damage, use of anticonvulsants for seizure prevention, concurrently using ketamine, symptomatic brain metastases.
- 3.26 Skin conditions such as open sores that would prevent proper application of the electrodes.
- 3.27 Other medical or other condition(s) that in the opinion of the investigators might compromise the objectives of the study.
- 3.28 Currently receiving gabapentin or pregabalin and not willing to be weaned off of these medications prior to Scrambler therapy initiation.
Note: It is OK to continue these medications in patients who are receiving TENS. (See [Appendix I](#)).
- 3.29a History of peripheral neuropathy prior to receiving neurotoxic chemotherapy.
- 3.29b Prior treatment with Scrambler therapy.

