4.0 Test Schedule

Use for first treatment period; repeat for second treatment period

Tests and procedures	Active Monitoring Phase				
	≤30 days prior to registration	Day 1, Prior to therapy	Daily for 14 consecutive days beginning on Day 1 of active therapy	Last day of assigned therapy (±1 day)	Weekly for 8 weeks
History and exam, PS ¹ , Eligibility questions ² (Appendix II: A or B)	X				
Pregnancy test ³		X			
Declaration of most problematic site (upper versus lower extremities) and most problematic symptom (tingling versus pain): Appendix III	X				
Pain/tingling questionnaire regarding the prior week (Appendix IV: A or B)		X ⁴			
Patient Questionnaire: Before each treatment (Appendix V: A or B)		X ⁵	X ⁵		
Patient Questionnaire: After each treatment (Appendix VI: A or B)			X ⁵		
EORTC CIPN 20 (Appendix VII)		X		X ⁶	X
Patient Questionnaire: Analgesic Use (Appendix VIII)		X	X		X
Patient Questionnaire After each therapy and during weekly follow-up: Global Impression of Change and Patient Preference (Appendix IX: A or B)			X ⁷		X ⁷
Daily Treatment Log and Adverse Assessment (Appendix X)			X		
Individual Patient Dermatome Map-Electrode Placement (Appendix XI) Scrambler only			X		
Audiovisual recordings ^R			X ⁸		
Weekly follow-up patient questionnaire (Appendix XII:A or B)					X ⁹
Written patient summary (if the patient is willing to provide) ^R					X ¹⁰
Research Blood draw for CBC/diff and mRNA ^{11,R}		X		X	
fMRI ^{12,R}		X		X	
Quantitative Sensory Testing ^{13,R}		X		X	

Tests and procedures	Active Monitoring Phase				
	≤30 days prior to registration	Day 1, Prior to therapy	Daily for 14 consecutive days beginning on Day 1 of active therapy	Last day of assigned therapy (±1 day)	Weekly for 8 weeks
Study Coordinator/Nurse phone call to discuss therapy and any concerns, record any adverse events that are reported and to remind the patient to complete questionnaires and mail them			X ¹⁴		X

Footnotes:

1. PS must be done ≤7 days prior to registration.
 2. Appendix II A or B, as labeled depending on neuropathy area type. (This evaluation is used for eligibility.)
 3. For women of childbearing potential only. Must be done prior to first Scrambler therapy (or the first day of the second treatment period, if Scrambler therapy is crossover).
NOTE: This testing is not needed for TENS therapy.
 4. Appendix IV A or B, as labeled depending on neuropathy area to be treated

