9.2 Gabapentinoid use

Patients should not receive gabapentinoids (e.g. Neurontin®, Lyrica®) during treatment with Scrambler therapy. If patients are on gabapentinoids at the time of registration and are randomized to Scrambler therapy, they must be weaned off prior to receiving Scrambler therapy.

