13.3 Cancel

A patient is deemed a *cancel* if he/she is removed from the study for any reason before any study treatment is given.

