16.32 Secondary efficacy endpoints

Perceived treatment efficacy from the Subjective Global Impression of Change instrument (Appendix IXA and B) will be summarized (median and range for impression of change and frequency for preference) by arm and compared

(Wicoxon rank-sum test for impression of change and Chi-square test for preference) between treatment arms.

EORTC CIPN20 scores and changes in scores will be summarized (mean, sd, median, range) at each time point by arm and will be compared between arms using two-sample t-tests.

- 16.33 Goal: Evaluate the tolerability of Scrambler therapy and compare it to TENS therapy, in this population.

Frequency and type of toxicities occurred during therapy will be summarized by treatment arm and compared between arms using Fisher-exact test.

- 16.34 Goal: Evaluate whether Scrambler therapy, compared to TENS therapy, can decrease the use of pain medication for CIPN.

Type and frequency of analgesic used will be summarized by treatment arms and will be compared using Fisher-exact test.

- 16.35 Goal: Explore whether mRNA gene expression changes are similar to that previously reported by Starkweather et al.

In a descriptive manner, the gene expression will be compared to what was previously reported.

- 16.36 Goal: Explore whether Scrambler therapy will change fMRI.

Changes in fMRI following Scrambler therapy will be described in the subset of patients selected for this component of the study.

- 16.37 Descriptive statistics will be used for the data from Quantitative Sensory Testing.

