Appendix I Patient instruction sheet for tapering gabapentin and pregabalin

Tapering of gabapentin or pregabalin will preferably occur over two weeks. Lower doses may be tapered over one week to accommodate patient availability with approval of [name]. During first week of taper, drug will be reduced approximately 25% for 3-4 days, then an additional 25% so that the drug has been reduced by approximately 50% by the end of the first taper week. Drug will continue to be reduced during the second week every few days until the final dose is taken the evening prior to treatment. Patient provider or [name] will need to be contacted if different doses of pills are needed. Patients will be instructed on potential symptoms of withdrawal and be asked to contact study staff if symptoms are experienced, as the taper may need to be adjusted. The decision of which dose to begin tapering (morning, noon, evening) will be decided between patient and study staff.

Patient Form

Gabapentin/Pregabalin (circle one)	mg	mg	mg	mg
Day/Date				
1= / /	pills	pills	pills	pills
2= / /	pills	pills	pills	pills
3= / /	pills	pills	pills	pills
4= / /	pills	pills	pills	pills
5= / /	pills	pills	pills	pills
6= / /	pills	pills	pills	pills
7= / /	pills	pills	pills	pills
8= / /	pills	pills	pills	pills
9= / /	pills	pills	pills	pills
10= / /	pills	pills	pills	pills
11= / /	pills	pills	pills	pills
12= / /	pills	pills	pills	pills
13= / /	pills	pills	pills	pills
14= / /	pills	pills	pills	pills
Day 1 of Treatment	0 pills	0 pills	0 pills	0 pills

Potential symptoms of gabapentin withdrawal may include nausea, insomnia, restlessness, agitation, anxiety, disorientation, confusion, light sensitivity, sweating, headaches, palpitations, chest pain, and flu-like symptoms.

**Appendix IIA Peripheral Neuropathy Questionnaire for Upper Extremity Neuropathy
(Used for Eligibility)**

Initials _____
Study # _____
Date _____
Day _____

How much of a problem has **pain** in your fingers or hands been **in the past week**?

0	1	2	3	4	5	6	7	8	9	10
No pain in fingers and/or hands										Pain in fingers and/or hands as bad as you can imagine

How much of a problem has **tingling** in your fingers or hands been **in the past week**?

0	1	2	3	4	5	6	7	8	9	10
No tingling in fingers and/or hands										Tingling in fingers and/or hands as bad as you can imagine

**Appendix IIB Peripheral Neuropathy Questionnaire for Lower Extremity Neuropathy
(Used for Eligibility)**

Initials _____
Study # _____
Date _____
Day _____

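### Harms of the gabapentinoid taper that precedes Scrambler only have no scheduled recording and fall outside the Goal 2 tolerability comparison

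*Combined protocol and SAP*

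**What the plan says.** **Who tapers.** Exclusion criterion 3.28 bars a patient who is "Currently receiving gabapentin or pregabalin and not willing to be weaned off of these medications prior to Scrambler therapy initiation". Its note adds: "It is OK to continue these medications in patients who are receiving TENS". Section 9.2 applies the requirement after allocation: users who "are randomized to Scrambler therapy, they must be weaned off prior to receiving Scrambler therapy".

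**When and with what risks.** Appendix I prefers a two-week taper, allows one week for lower doses, and places the last dose on the evening before treatment. It lists 13 possible withdrawal symptoms, among them disorientation, confusion, palpitations and chest pain. On reporting it says "Patients will be instructed on potential symptoms of withdrawal and be asked to contact study staff if symptoms are experienced", so that the taper can be adjusted. The patient form has columns for pill counts only.

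**What is analysed.** For Goal 2, Section 16.33 reads: "Frequency and type of toxicities occurred during therapy will be summarized by treatment arm", followed by a Fisher exact comparison between arms. Under 13.3, a cancel is a patient "removed from the study for any reason before any study treatment is given".

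**The concern.** The taper is something the protocol makes patients do, in one arm, after randomisation. Goal 2 expects Scrambler to be well tolerated, with side effects not substantially different from those of TENS. If a harm that only the Scrambler path requires arises before the counting window opens, the comparison omits it, and the omission favours Scrambler.

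The gap can also work the other way. With no symptom grading at baseline, a withdrawal symptom still present on Day 1 looks like a new event on therapy and may be attributed to the device. In both cases the tolerability table would not show what the taper did and what the device did.

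**Working it through.** The documents give no operating figure for the tolerability comparison or the pause rule, so there is none to reproduce on this point. Table 16.51 concerns the primary endpoint only. It reproduces (pooled normal approximation, one-sided 0.05, 25 per arm: 80.7, 80.4, 81.7, 81.3 and 82.1%, against the printed 80, 80, 81, 81 and 82%) and is unaffected.

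**1. Timeline against scheduled adverse-event capture**

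| Period | Protocol activity | Scheduled capture |
|---|---|---|
| Registration to Day 1, up to 50 days (6.5) | Scrambler users taper over 7 to 14 days; nothing comparable is required for TENS | None. The Section 4.0 schedule has no column here; the Day 1 pre-therapy column has no adverse-event item; the adverse-event form is not among the initial materials (18.11) |
| Daily schedule, 14 days from Day 1 | Assigned therapy | Daily log (Appendix X); for TENS, calls on Day 2 and once on Days 8–10; adverse-event form (18.12) |
| Eight weeks of follow-up | Observation | Weekly call; adverse-event form (18.12) |

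Section 10.3 sets pretreatment CTCAE grading to none.

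**2. What happens to a taper event**

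- *Before Day 1, and the patient goes on to Scrambler:* outside the on-therapy window of 16.33.
- *Before Day 1, and the patient leaves:* a cancel under 13.3; also outside 16.33.
- *Persisting past Day 1:* open to the daily log and to 16.33, but with no baseline grade to show that it came first.
- *Grade 3 or 4 at any time:* reportable under 10.312 whatever the attribution, if staff learn of it.
- *Grade 2:* reportable under 10.311 only if judged at least possibly related to the study treatment or procedure. Section 10.13 opens with treatment or procedure, but its category definitions name the investigational agent(s). Neither section mentions the taper.

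**3. Scale of exposure.** The share of users, q, is not given. Assuming 20%, 40% or 60%, expected users in the Scrambler arm are 25 × q = 5, 10 or 15. Each affected patient is 1/25 = 4 percentage points of the arm.

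**4. How many omitted events would matter.** For k v 0 events with 25 per arm, the two-sided Fisher p is 2 × C(25,k)/C(50,k):

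- k = 5: 2 × 53,130/2,118,760 = 0.050 (0.0502, just above 0.05)
- k = 6: 2 × 177,100/15,890,700 = 0.022

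So six affected patients against none would take the comparison below 0.05. Let r be the assumed chance of a pre-Day-1 taper event of any grade in a user. With independent patients and no TENS events, P(6 or more of 25), binomial with p = q × r, is:

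| q | r | p | P(≥ 6 of 25) |
|---|---|---|---|
| 20% | 30% | 0.06 | 0.3% |
| 40% | 50% | 0.20 | 38% |
| 60% | 50% | 0.30 | 81% |

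**5. Pause rule (16.82), three or more of the first ten treated with a related Grade 3+ event.** Assume a device-related Grade 3+ rate of 2% and let r now be the Grade 3+ taper rate in users, so p = 1 − 0.98 × (1 − q × r). If taper events are not counted, P(≥ 3 of 10) = 0.1%. If they are, it is 0.3% (q = 20%, r = 5%), 1.8% (40%, 10%) or 14.9% (60%, 20%).

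**The case against.** The strongest reply is that counting toxicity on therapy is a legitimate choice in a trial that Section 16.5 calls non-confirmatory, and that Goal 2 is about tolerability of the therapy, not of a washout. That is fair as far as it goes: the on-therapy table should stay. It does not explain why a harm that the protocol itself can cause in one arm should appear in no planned table.

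A reader might also infer more than the documents support:

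- *That adverse events are collected only from Day 1.* Only the scheduled assessments and the form timing start there. Section 10.31 has no start date.
- *That a Grade 2 withdrawal event would be scored unrelated.* It could be. Sections 10.11, 10.13 and 10.311 all speak of a treatment or procedure, so an investigator could judge the taper to be one. The text is silent, not adverse.
- *That the pause rule shuts taper events out.* Section 16.82 has no Day 1 limit, and a patient who tapers and then starts Scrambler is a treated patient; only cancels are clearly outside. Sections 16.81 and 16.84 and the monitoring board's review in 16.7 add further safeguards.
- *That all taper harm is lost, or that patients are unwatched.* The last dose falls the evening before Day 1, so later symptoms can be logged. Patients are told what to look for and whom to contact, and leaving before treatment is documented on the cancel notification (18.11).
- *That tapers before crossover enlarge the bias.* The second period is exploratory (16.2), and such tapers may overlap weekly calls that record events.

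Finally, the effect may be nil: at 20% users, about five patients are exposed, and even if all five had an event against none on TENS, p would be 0.050, not below 0.05.

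**Conclusion.** The point holds for scheduled recording and for the Goal 2 comparison. The taper is required in one arm after randomisation, no adverse-event assessment is scheduled while it runs, and 16.33 does not take in events before therapy. Those omissions favour Scrambler; symptoms carried past Day 1 may count against the device. The text also leaves open whether a taper event is related to study treatment or procedure.

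The size cannot be derived from the documents. The figures above rest on assumed user shares and withdrawal rates, on every counted taper event falling before Day 1, and on no events in TENS. They show only that about six omitted patients would be enough to change the tolerability test, which is unlikely if users are few and quite possible if use and withdrawal are both common. The effect on the pause rule is probably small. The primary-endpoint analysis is not touched by this point. The case for change is that a stated goal and safety reporting are affected and the remedy is cheap.

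**What to change.** - **Collection.** Record adverse events from randomisation in both arms. Add a symptom and adverse-event line to the Appendix I form. Add one pre-treatment question on Day 1, asked of both arms, covering the interval since randomisation. Reflect this in Sections 4.0 and 18.
- **Attribution.** State in 10.13 and 10.311 that events at least possibly related to the protocol-required taper are related to a study procedure.
- **Pause rule.** State in 16.82 whether such events count. Leave the treated-patients denominator as it is; adding taper starters in one arm would make the first-ten rule ill-defined.
- **Analysis.** In 16.33, keep the on-therapy table and place beside it a by-arm table of adverse events from randomisation, with cancels for adverse events included. Report the length of the pre-treatment interval in each arm, since it can run to 50 days under 6.5 and may differ between arms.

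The cost is one line on an existing form, one Day 1 question, one extra table and short wording changes. The downside is a little more data collection, and Scrambler's adverse-event rate may look less favourable. No change to the taper is proposed.

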Appendix III Declaration of most problematic site and symptom

Most problematic symptom:

- Pain
- Tingling

Most problematic site:

- Upper extremities
- Lower extremities

Initials _____
Study # _____
Date _____
Day _____

Appendix IVA Peripheral Neuropathy Questionnaire for Upper Extremity Neuropathy

Everyone has aches and pain at some time. We are interested in your experience of numbness, tingling and pain that you have developed related to chemotherapy.

Initials _____
Study # _____
Date _____
Day _____

How much of a problem has **pain** in your fingers or hands been **in the past week**?

0	1	2	3	4	5	6	7	8	9	10
No pain in fingers and/or hands										Pain in fingers and/or hands as bad as you can imagine

How much of a problem has **tingling** in your fingers or hands been **in the past week**?

0	1	2	3	4	5	6	7	8	9	10
No tingling in fingers and/or hands										Tingling in fingers and/or hands as bad as you can imagine

How much of a problem has **numbness** in your fingers or hands been **in the past week**?

0	1	2	3	4	5	6	7	8	9	10
No numbness in fingers and/or hands										Numbness in fingers and/or hands as bad as you can imagine

Appendix IVB Peripheral Neuropathy Questionnaire for Lower Extremity Neuropathy

Everyone has aches and pain at some time. We are interested in your experience of numbness, tingling and pain that you have developed related to chemotherapy.

Initials _____
Study # _____
Date _____
Day _____

How much of a problem has **pain** in your toes or feet been **in the past week**?

0	1	2	3	4	5	6	7	8	9	10
No pain in toes and/or feet										Pain in toes and/or feet as bad as you can imagine

How much of a problem has **tingling** in your toes or feet been **in the past week**?

0	1	2	3	4	5	6	7	8	9	10
No tingling in toes and/or feet										Tingling in toes and/or feet as bad as you can imagine

How much of a problem has **numbness** in your toes or feet been **in the past week**?

0	1	2	3	4	5	6	7	8	9	10
No numbness in toes and/or feet										Numbness in toes and/or feet as bad as you can imagine

Appendix VA Patient Questionnaire: Before Each Treatment for Upper Extremity Neuropathy

Everyone has aches and pains at some time. We are interested in your experience of numbness, tingling and pain that you have developed related to chemotherapy.

Please address these questions related to this. Please comment only on symptoms in the primarily treated area.

Initials _____
Study # _____
Date _____
Day _____

Directions: Please answer the following questions:

1. How much **numbness** do you have in your fingers or hands **right now** (circle one number)?

0 1 2 3 4 5 6 7 8 9 10
None **As bad
as can be**

2. How much **numbness** have you had in your fingers or hands **at its worst over the past 24 hours** (circle one number)?

0 1 2 3 4 5 6 7 8 9 10
None **As bad
as can be**

3. How much **numbness** have you had in your fingers or hands **on average over the past 24 hours** (circle one number)?

0 1 2 3 4 5 6 7 8 9 10
None **As bad
as can be**

4. How much **tingling** do you have in your fingers or hands **right now** (circle one number)?

0 1 2 3 4 5 6 7 8 9 10
None **As bad
as can be**

5. How much **tingling** have you had in your fingers or hands **at its worst over the past 24 hours** (circle one number)?

0 1 2 3 4 5 6 7 8 9 10
None **As bad
as can be**

6. How much **tingling** have you had in your fingers or hands **on average over the past 24 hours** (circle one number)?

0 1 2 3 4 5 6 7 8 9 10
None **As bad
as can be**

7. How much **pain** do you have in your fingers or hands **right now** (circle one number)?

0 1 2 3 4 5 6 7 8 9 10
None **As bad
as can be**

Appendix VB Patient Questionnaire: Before Each Treatment for Lower Extremity Neuropathy

Everyone has aches and pains at some time. We are interested in your experience of numbness, tingling and pain that you have developed related to chemotherapy.

Initials _____
Study # _____
Date _____
Day _____

Please address these questions related to this. Please comment only on symptoms in the primarily treated area.

Directions: Please answer the following questions:

1. How much **numbness** do you have in your toes or feet **right now** (circle one number)?

0 1 2 3 4 5 6 7 8 9 10
None **As bad
as can be**

2. How much **numbness** have you had in your toes or feet **at its worst over the past 24 hours** (circle one number)?

0 1 2 3 4 5 6 7 8 9 10
None **As bad
as can be**

3. How much **numbness** have you had in your toes or feet **on average over the past 24 hours** (circle one number)?

0 1 2 3 4 5 6 7 8 9 10
None **As bad
as can be**

4. How much **tingling** do you have in your toes or feet **right now** (circle one number)?

0 1 2 3 4 5 6 7 8 9 10
None **As bad
as can be**

5. How much **tingling** have you had in your toes or feet **at its worst over the past 24 hours** (circle one number)?

0 1 2 3 4 5 6 7 8 9 10
None **As bad
as can be**

6. How much **tingling** have you had in your toes or feet **on average over the past 24 hours** (circle one number)?

0 1 2 3 4 5 6 7 8 9 10
None **As bad
as can be**

Appendix VIA **Patient Questionnaire: Immediately Post Therapy for Upper Extremity Neuropathy**

Everyone has aches and pain at some time. We are interested in your experience of numbness, tingling and pain that you have developed related to chemotherapy.

Initials _____
Study # _____
Date _____
Day _____

Please complete questionnaire immediately after each daily treatment session. Please comment only on symptoms in the primarily treated area.

Directions: Please answer the following questions:

1. How much **numbness** do you have in your fingers or hands **right now** (circle one number)?

0	1	2	3	4	5	6	7	8	9	10
None										As bad as can be

2. How much **tingling** do you have in your fingers or hands **right now** (circle one number)?

0	1	2	3	4	5	6	7	8	9	10
None										As bad as can be

3. How much **pain** do you have in your fingers or hands **right now** (circle one number)?

0	1	2	3	4	5	6	7	8	9	10
None										As bad as can be

Appendix VIB Patient Questionnaire: Immediately Post Treatment for Lower Extremity Neuropathy

Everyone has aches and pain at some time. We are interested in your experience of numbness, tingling and pain that you have developed related to chemotherapy.

Initials _____
Study # _____
Date _____
Day _____

Please complete questionnaire immediately after each daily treatment session. Please comment only on symptoms in the primarily treated area.

Directions: Please answer the following questions:

1. How much numbness do you have in your toes or feet right now (circle one number)?
0 1 2 3 4 5 6 7 8 9 10
None As bad as can be

2. How much tingling do you have in your toes or feet right now (circle one number)?
0 1 2 3 4 5 6 7 8 9 10
None As bad as can be

3. How much pain do you have in your toes or feet right now (circle one number)?
0 1 2 3 4 5 6 7 8 9 10
None As bad as can be

